4.5 Permissible and Prohibited Medications/Treatments

4.5.1 Permissible Medications/Treatments

Therapy considered necessary for the patient's welfare may be given at the discretion of the investigator. Patients should be instructed to maintain a stable dose during the study whenever possible. All medications and adjunct therapies should be recorded on the appropriate electronic case report form (eCRF). If the permissibility of a specific medication/treatment is in question, please contact Allergan.

If the patient is already using psychiatric medications or medications for attention deficit hyperactivity disorder, they should have been on a stable dose prior to randomization/day 1 and agree to remain on the same dose during the study if possible when medically indicated.

Use of antihistamines and/or decongestants (sympathomimetics) is permitted to treat upper respiratory infections or allergies after study treatment has been administered.

Refer to Section 5.9.3 for information on permitted study treatment anesthesia.

If the permissibility of a specific medication/treatment is in question, please contact Allergan.

4.5.1.1 Definition of Females of Childbearing Potential and/or Acceptable Contraceptive Methods

For females of childbearing potential (ie, females who are postmenarche), the following methods of contraception, if properly used, are generally considered reliable: oral contraceptives, patch contraceptives, injection contraceptives, implantable contraceptives, male condom with intravaginal spermicide, diaphragm or cervical cap with spermicide, vaginal contraceptive ring, intrauterine device, surgical sterilization (bilateral tubal ligation), vasectomized partner, or sexual abstinence (when this is the lifestyle of the patient).

If a postmenarche female patient is sexually active, the investigator and each patient (and her parent/legally authorized representative, in accordance with local laws and IRB/IEC requirements) will determine the appropriate method of contraception to be used during the study.

If a female becomes pregnant during the study, the investigator will notify Allergan immediately after the pregnancy is confirmed and the patient will be exited from the study after appropriate safety follow-up, which must be at least 12 weeks since study treatment. The investigator will: (1) notify the patient's physician that the patient has been treated with

BOTOX, and (2) follow the progress of the pregnancy. The investigator must document the outcome of the pregnancy and provide a copy of the documentation to Allergan.

4.5.2 Prohibited Medications/Treatments

The decision to administer a prohibited medication/treatment is done with the safety of the study participant as the primary consideration. When possible, Allergan should be notified before the prohibited medication/treatment is administered.

Botulinum toxin treatment of any serotype other than study drug is prohibited for any indication. Immunization to any botulinum toxin serotype is also prohibited during the study.

Anticholinergics or any other medications (including sympathomimetic medications) used for the treatment of symptoms of OAB, including nocturnal enuresis or nocturia, are prohibited throughout study participation. Desmopressin use is prohibited within 1 day of the start of the screening period procedures. Anticholinergic therapy is prohibited within 7 days of the start of the screening period procedures, or within 4 weeks if administered intravesically. Mirabegron is prohibited within 14 days of the start of the screening period procedures.

Administration of intravesical capsaicin or resiniferatoxin is prohibited during the study.

Use of electrical stimulation and neuromodulation devices (implanted and external) for the treatment of OAB are prohibited during study participation (if a patient is enrolled into the study with a device still implanted, it must be inactive at least 4 weeks prior to the first screening procedure; if a nonimplantable device is used, it must be discontinued at least 7 days prior to the first screening procedure).

Use of aminoglycoside antibiotic therapy is not permitted during study treatment administration. If a patient requires aminoglycoside antibiotic therapy during the trial, any study treatment administration must be delayed until the aminoglycoside antibiotic therapy is completed. Use of aminoglycoside antibiotics should also be avoided for 8 weeks after study treatment. Examples of such medications are: amikacin sulfate, gentamicin sulfate, kanamycin, tobramycin, netilmicin sulfate, and streptomycin.

Anticoagulant medications (eg, warfarin and other Coumadin derivatives), antiplatelet medications (eg, clopidogrel and aspirin [including low dose]) and any other medications with anticoagulative effects (eg, nonsteroidal anti-inflammatory drugs) are prohibited for a minimum of 3 days (or longer according to the clinical judgment of the investigator) prior to any study treatment, and must not be recommenced until the day following treatment.

Neuromuscular blocking agents may not be administered at the same time as the study treatment.

5. Study Treatments

5.1 Study Treatments and Formulations

BOTOX

Each vial of BOTOX (Botulinum Toxin Type A) purified neurotoxin complex, formulation No. 9060X (US Adopted Name is OnabotulinumtoxinA), contains: 100 U of *Clostridium botulinum* toxin Type A, 0.5 mg albumin (human), and 0.9 mg sodium chloride in a sterile, vacuum-dried form without a preservative. One unit corresponds to the calculated median lethal dose (LD₅₀) in mice of the reconstituted BOTOX injected intraperitoneally. The study medication will be reconstituted with 0.9% sodium chloride (preservative-free).

5.2 Control Treatment

There is no control treatment in this study.

5.3 Methods for Blinding

Both patients and investigators will remain blinded to BOTOX dosage (unless the patient is requested to exit the study via the IVRS/IWRS due to dosing request, as described at the end of Section 5.5).

The study medication will be packaged and labeled in identically appearing vials and reconstituted to the same volume by an independent drug reconstitutor (IDR) who is not associated or involved with a study patient's care or study assessments, with the exception of study medication preparation. The study medication will be identified as an investigational compound and the carton will also be labeled with the study number and kit number.

5.4 Treatment Allocation Ratio and Stratification

Patients will be randomized centrally and assigned a randomization number prior to treatment. In addition, patients will be stratified by the number of daytime urinary urgency incontinence episodes reported at baseline (a total of ≤ 6 or > 6 episodes over the 2-day diary). One randomization number will be assigned to each patient prior to treatment and will be associated with 25 U, 50 U, or 100 U BOTOX in a 1:1:1 ratio.

5.5 Method for Assignment to Treatment Groups/Randomization

Following the screening period, patients who meet the study inclusion/exclusion criteria and the day of treatment criteria (see Section 5.9.1) will be assigned a randomization number through the IVRS/IWRS. Study medication will be labeled with medication kit numbers and the IVRS/IWRS will provide the IDR with a specific medication kit number and treatment group assignment for the patient.

Patients who request and qualify for retreatment will receive a blinded dose of 25 U BOTOX (not to exceed 6 U/kg), 50 U BOTOX (not to exceed 6 U/kg), or 100 U BOTOX (not to exceed 6 U/kg). The dose received will be dependent on the assessment of the clinical response (efficacy and safety) to the previous blinded study treatment. The patient/parent/legally authorized representative will be questioned on the patient's treatment response to establish if, in their opinion, the current treatment response is adequate or if there was little or no treatment benefit and whether they would be willing/want to move to a higher dose. They will also be questioned on whether the patient is experiencing side effects. Using this information, the investigator will use his/her own clinical assessment of the patient and apply the following criteria for the retreatment dose request:

- if the benefit/risk balance is evaluated by the investigator to be appropriate at the current dose, then the same dose would be requested
- if the investigator assessed that, although the preceding dose was well tolerated, the response received was insufficient and warrants a higher dose, then a dose increase would be requested
- if the investigator assessed that there were side effects that would warrant a lower dose, the patient would be exited from the study

Compared with the previous treatment, the investigator therefore has the following options:

- elect to keep the same dose as received at the previous treatment (not to exceed 6 U/kg)
- elect to increase the dose compared to the previous treatment (not to exceed 6 U/kg):
 - if the patient received 25 U BOTOX at the previous treatment, they would receive 50 U BOTOX
 - if the patient received 50 U BOTOX at the previous treatment, they would receive 100 U BOTOX
 - if the patient received 100 U BOTOX at the previous treatment, they would remain at 100 U BOTOX (after 2 requests, when the patient has already received 2 treatments of 100 U BOTOX, they would be exited; see below)

At the qualification for retreatment visit the investigator or designee will contact the IVRS/IWRS and indicate the treatment option for the patient. IVRS/IWRS options will be either to remain at the same dose or to increase the dose since patients will be exited from the study if the investigator assessed that a lower dose was warranted (see below).

In the following 2 scenarios, patients will be exited once a minimum of 12 weeks of follow-up since their last treatment has occurred:

- for any patient who is already on the highest dose (100 U), if a dose escalation is requested by the investigator on 2 occasions, the patient will be exited from the study upon the second escalation request without receiving any further treatments
- for any patient on any dose, if the investigator assesses that they should not be retreated with the current dose but that a dose reduction would be warranted, the patient will be exited from the study as a reduction of dose in this study is not an option

Once all “day of treatment criteria” have been met at the day of treatment visit, the study medication will be allocated via IVRS/IWRS. Study medication will be labeled with medication kit numbers and the IVRS/IWRS will provide the IDR with a specific medication kit number and treatment group assignment for the patient.

Note that retreatments will be blinded until completion of the primary analysis, after which time the investigators will be unblinded to the patients’ initial treatment assignments (see Section 7).

5.6 Treatment Regimen and Dosing

Patients can receive multiple retreatments in this study.

All eligible patients enrolled into the study will receive a double-blind treatment of either 25 U BOTOX (not to exceed 6 U/kg), 50 U BOTOX (not to exceed 6 U/kg), or 100 U BOTOX (not to exceed 6 U/kg) for treatment 1.

All patients eligible for retreatment will receive either 25 U BOTOX (not to exceed 6 U/kg), 50 U BOTOX (not to exceed 6 U/kg), or 100 U BOTOX (not to exceed 6 U/kg). The dosage used at each retreatment will be determined as described in Section 5.5.

To qualify for retreatment a patient must fulfill the qualification for retreatment criteria (see Section 5.10.1 for details).

Each retreatment will also require all the “day of treatment criteria” to be fulfilled (see Section 5.9.1 for details).

5.7 Storage of Study Medications

The study medication must be stored in a secure area and administered only to patients entered into the clinical study, at no cost to the patient, in accordance with the conditions specified in this protocol.

The vacuum-dried study medication must be stored in a refrigerator at a temperature between 2 and 8°C. Refer to the Pharmacy Manual for guidelines on acceptable variances and instructions for reporting to Allergan. If not used immediately (ie, within 30 minutes of reconstitution) reconstituted study medication, either in the vial or the dosing syringe, must also be stored in a refrigerator at a temperature between 2 and 8°C, and is to be used within 4 hours following reconstitution. Storage conditions will be documented. If not used within 4 hours of reconstitution, study medication should be disposed of as described in the Pharmacy Manual.

5.8 Preparation of Study Medications

Study medication should be prepared once all the “day of treatment criteria” have been fulfilled, and the IVRS/IWRS has been contacted. Instructions for the reconstitution and preparation of study medication are provided in the Pharmacy Manual.

An IDR must prepare the study medication. The IDR must be trained and have the skills necessary to prepare the study medication (eg, pharmacist, nurse, study coordinator). This person must not be associated or involved with a study patient’s care or study assessments, with the exception of study medication preparation.

5.9 Treatment Administration

5.9.1 Day of Treatment Criteria

Administration of the first study treatment should occur within 28 days of the start of the screening procedures. For patients who request retreatment, study treatment will be administered within 4 weeks of qualification for retreatment (see Section 5.10.1 for qualification for retreatment criteria), but no later than 96 weeks since study enrollment on day 1 of this study. The following “day of treatment criteria” must be fulfilled prior to the administration of study medication:

- central laboratory urine analysis results and, if applicable, urine culture and sensitivity results for possible UTI have been reviewed
- negative urine dipstick reagent strip test (for nitrites and leukocyte esterase) on the day of treatment
- patient is asymptomatic for a UTI on the day of treatment, in the opinion of the investigator
- appropriate prophylactic antibiotics have been initiated (see Section 5.9.2)
- antiplatelet or anticoagulant therapy or medications with anticoagulative effects have been discontinued at least 3 days prior to treatment
- negative urine pregnancy result (for postmenarche females)
- for patients who request retreatment, PVR urine volume confirmed to be < 200 mL at the qualification for treatment visit
- investigator continues to deem treatment is appropriate and no condition or situation exists which, in the investigators opinion, puts the patient at significant risk from receiving treatment

Note: If a patient does not fulfill the “day of treatment criteria” they would still be considered qualified for retreatment (ie, qualification for retreatment or any associated procedures are not to be repeated). The treatment administration visit would be rescheduled for as soon as possible (if applicable), and the “day of treatment criteria” would need to be fulfilled prior to treatment administration.

5.9.2 Prophylactic Antibiotics

All patients must receive prophylactic antibiotics prior to each treatment administration. The approach is dependent upon the clinical judgment of the investigator, but could include either an intravenous (IV) or intramuscular (IM) dose of antibiotics prior to treatment administration on day 1 or oral antibiotics for at least 1 to 3 days prior to treatment and on the day of treatment. Antibiotics could also be continued for 1 to 3 days posttreatment (or longer).

Note: Independent from the above description for prophylactic antibiotics, if a UTI is identified from the urinalysis/culture obtained during the screening period, the UTI must be treated with an antibiotic to which the identified bacteria is sensitive per local site practice. As per the day of treatment criteria described in Section 5.9.1, the patient must not have a UTI on the day of treatment, in the opinion of the investigator.

5.9.3 Use of Anesthesia

Anesthesia will be used for all patients during the treatment administration. The choice of general or local anesthesia is at the discretion of the investigator and the preference of the patient/legally authorized representative.

If general anesthesia is to be used it will be administered per local site practice (including prior sedation if deemed medically necessary) by an appropriately qualified anesthesiologist; however the use of neuromuscular blocking agents is not permitted.

Patients who undergo the treatment procedure under local anesthesia may do so with or without sedation at the discretion of the investigator and per local site practice. Local anesthesia of the bladder will be achieved by instillation of 1% to 2% lidocaine (or similar acting local anesthetic) into the bladder prior to the procedure. The instillation solution should remain in the bladder for at least 15 minutes in order to achieve sufficient anesthesia. The bladder will then be drained of lidocaine, rinsed with saline, and drained again.

The following are permitted to facilitate the insertion/removal of the cystoscope:

- lubricating gel
- local anesthesia to the urethra: intraurethral lidocaine gel (or similar local anesthetic gel)

5.9.4 Treatment Procedure

A rigid or flexible cystoscope may be used for study treatment administration. As described above, lubricating gel and intraurethral lidocaine (or similar) can be used to facilitate cystoscope insertion. The bladder should be instilled with a sufficient amount of saline in order to achieve adequate visualization for the study injections.

The injection of study medication must not occur if bladder stones have been identified during the screening period from the bladder scan/ultrasound or on the day of treatment upon cystoscopy at the time of injection).

The investigator will receive one 10 mL syringe prefilled with 10 mL of study medication, and one 1 mL syringe prefilled with saline.

The 10 mL of study drug will be administered as 20 injections each of 0.5 mL. Under direct cystoscopic visualization, injections should be distributed evenly across the detrusor wall and spaced approximately 1 cm apart. To avoid injecting the trigone, the injections should be at least 1 cm above the trigone (see the Study Treatment Injection Pattern diagram in Attachment 12.2). The injection needle should be filled (primed) with approximately 1 mL

of reconstituted study medication prior to the start of injections (depending on needle length) to remove any air. The injection needle should be inserted approximately 2 mm into the detrusor for each injection. For the final injection site, a sufficient amount of saline (from the prefilled 1 mL syringe) will be flushed through the injection needle to deliver the small amount of study medication remaining in the needle. This will ensure that the entire volume of study medication is administered to the patient.

After the injections are given, the saline used for visualization should be drained from the bladder. Patients should remain in the clinic under observation for at least 30 minutes and until a spontaneous void has occurred (or longer, depending upon local site practice). Safety monitoring and assessments are to be done according to local site practice (eg, monitoring of blood pressure, pulse rate). Prior to leaving the study clinic, patients/parents/legally authorized representatives will be instructed to contact the study site if the patients experience any adverse events posttreatment.

The investigator, or designee, will be required to document on the study treatment eCRF whether the study drug administration was performed as indicated above. In addition, details on equipment used (eg, rigid or flexible cystoscope) will be recorded.

5.10 Retreatment

Patients can receive multiple retreatments in this study (between 1 and 7 at 25 U, 50 U, or 100 U BOTOX; not exceeding 6 U/kg). For each retreatment, patients must fulfill the qualification for retreatment criteria described in Section 5.10.1. In addition, prior to treatment administration the day of treatment criteria must be fulfilled, as described in Section 5.9.1.

5.10.1 Qualification for Retreatment Criteria

At each follow-up clinic visit and telephone contact from week 12 after each treatment onward, the patient's treatment response will be discussed with the patient/parent/legally authorized representative.

Patients/parents/legally authorized representatives can request retreatment at any scheduled clinic or telephone visit from week 12 onwards, or between scheduled visits. If the request is made at a scheduled clinic visit and all qualification for retreatment criteria are fulfilled, that visit then becomes a qualification for retreatment visit and the additional procedures will be performed. If the request occurs at a scheduled telephone visit or between visits, a qualification for retreatment clinic visit should be conducted within approximately 1 to

2 weeks of the request and the qualification for retreatment criteria should be assessed prior to performing any other procedures. The reason for the request will be collected.

In order to qualify for retreatment, the criteria listed below must be fulfilled at the qualification for retreatment visit:

- patient/parent/legally authorized representative requests retreatment
- patient has at least 1 daytime urinary urgency incontinence episode over the 2-day bladder diary collection period
- PVR urine volume must be < 200 mL
- at least 12 weeks have elapsed since previous treatment
- patient has not experienced a treatment-related serious adverse event at any time

Once these criteria are fulfilled, the patient is considered qualified for retreatment; this does not need to be repeated (or any of the associated qualification for retreatment procedures) if the patient does not get treated at the subsequent treatment visit or the treatment visit is delayed.

6. Response Measures and Summary of Data Collection Methods

6.1 Efficacy Measures

6.1.1 Primary Efficacy Measure

The primary efficacy measure is the number of daytime urinary incontinence episodes as recorded in the 2-day bladder diary during the week preceding each study visit. The primary timepoint is week 12 after treatment 1. For patients who receive multiple treatments in this study, the timepoint of main focus is week 12 after each treatment.

6.1.2 Secondary Efficacy Measures

The following secondary efficacy measures will be collected after each treatment using the bladder diary:

- number of daytime micturition episodes
- number of daytime urgency episodes
- presence or absence of night time urinary incontinence
- volume voided per micturition

In addition, the following duration of effect measures are considered secondary efficacy measures:

- time to patient request and time to patient qualification for retreatment

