adjust for multiplicity will be used. A similar analysis, without a hierarchical testing strategy, will be applied to other timepoints and to the secondary efficacy variables (pairwise comparisons will be done up to week 12).

For later BOTOX treatment cycles, week 12 after each treatment will be the timepoint of main interest and the efficacy variable of key focus is again change from study baseline in the daily average frequency of normalized daytime urinary incontinence episodes. For each BOTOX treatment cycle, descriptive statistics will be provided for the daily average frequency of normalized daytime urinary incontinence episodes at study baseline and each posttreatment visit. The change from study baseline and the 95% confidence intervals (CI) of the mean change will be provided.

Other efficacy analyses for the primary efficacy variable will include the proportion of patients achieving $\geq 50\%$, $\geq 75\%$, $\geq 90\%$, and 100% reduction from study baseline in daily average frequency of normalized daytime urinary incontinence at week 12 posttreatment 1. For BOTOX treatment cycle 1, the 100 U and 50 U BOTOX dose groups will be compared to the 25 U BOTOX group using the Cochran-Mantel-Haenszel (CMH) method controlling for baseline daytime urinary urgency incontinence episodes (a total of ≤ 6 episodes or > 6 episodes over the 2-day diary collection period).

Duration of effect will be evaluated as time from study drug administration to: a) patient's first request for subsequent treatment and b) qualification for subsequent treatment using a Kaplan-Meier survival analysis. Dose-response analyses will include a nonparametric area under the curve (AUC) analysis of daily average frequency of normalized daytime urinary incontinence episodes up to week 12 posttreatment 1.

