7.2.2 Secondary Efficacy Variables

There are 6 secondary efficacy variables assessed at the week 12 primary timepoint:

- change from baseline in daily average frequency of daytime micturition episodes
- change from baseline in daily average frequency of daytime urgency episodes
- presence or absence of night time urinary incontinence
- volume voided per micturition
- change from baseline in PinQ total score and item scores for 3 prespecified PinQ items (worry about smell, being with friends, and feel bad about myself)
- proportion of patients with a positive treatment response on the modified TBS (ie, rating their condition “greatly improved” or “improved”)

No imputation will be done for the missing values of the secondary efficacy variables.

The presence/absence of night time urinary incontinence will be based on the response to the question asked each morning in the bladder diary as to whether the patient had urinary incontinence during the night.

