7.3.2.2 Efficacy Analyses for the Secondary Efficacy Variables

The analysis of daytime micturition episodes, daytime urgency episodes, and volume voided per micturition at week 12 after treatment 1 will generally be analyzed as described for the primary efficacy endpoint in Section 7.3.1 except that baseline daytime urinary urgency incontinence episodes (a total of ≤ 6 episodes or > 6 episodes over the 2-day diary collection period) will be included in the ANCOVA model as an additional factor. The hierarchal testing strategy described in Section 7.3.1 will not be implemented.

For the analysis of night time urinary incontinence, the numbers and proportions of patients who experienced night time urinary incontinence on 0, 1, or 2 nights will be presented.

Analysis of time to patient request for retreatment and time to patient qualification for retreatment will be performed as described in Section 7.3.3.9, Duration of Effect.

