#### **5.1 Collection of Primary Efficacy Measurement(s) and Derivation of Primary Efficacy Variable(s)**

The following efficacy measures will be collected and summarized by BOTOX treatment cycle, BOTOX dose group, and all BOTOX group on the BOTOX-treated population:

- number of daytime urinary incontinence episodes
- number of daytime micturition episodes
- number of daytime urgency episodes
- presence or absence of nighttime urinary incontinence
- volume voided per micturition
- time to patient's request and time to patient's qualification for retreatment
- pediatric incontinence questionnaire (PinQ) score
- modified treatment benefit scale (TBS)

Change from study baseline analyses will be performed. Study baseline is defined as the data collected prior to the first treatment.

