#### 5.4.4 Night Time Urinary Incontinence Episodes

For each treatment cycle, a summary table for the number and proportion of patients who experienced nighttime urinary incontinence on 0, 1, or 2 nights will be presented by treatment group for study baseline and each post-treatment visit.

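### Night-time incontinence, one of the six week 12 secondary efficacy variables, is reported only as counts by dose group, with no dose comparison, no confidence interval and no patient-level link to baseline

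*Protocol*

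**What the plan says.** Protocol 6.1.2 names "presence or absence of night time urinary incontinence" as a secondary efficacy measure. Protocol 7.2.2 then says: "There are 6 secondary efficacy variables assessed at the week 12 primary timepoint", and night-time incontinence is one of them.

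The specific analysis text is short. Protocol 7.3.2.2 says that "the numbers and proportions of patients who experienced night time urinary incontinence on 0, 1, or 2 nights will be presented". SAP 5.4.4 says that "a summary table for the number and proportion of patients who experienced nighttime urinary incontinence on 0, 1, or 2 nights will be presented", by dose group, at study baseline and at each visit. Neither section names a test, a dose contrast, an interval, a covariate or a within-patient shift.

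Three general statements point further:

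- The Protocol Summary, after describing the primary ANCOVA, says: "A similar analysis, without a hierarchical testing strategy, will be applied to other timepoints and to the secondary efficacy variables". It adds that pairwise comparisons run up to week 12.
- Protocol 7.3.3.1 refers to between-group evaluations of the secondary variables up to week 12, as set out in Section 7.3.2.
- SAP 5.1 lists this variable among the efficacy measures and then states: "Change from study baseline analyses will be performed".

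SAP 13 records no deviations from the protocol.

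**The concern.** A variable given secondary status should support some statement about dose, because the three arms differ only in dose. As planned, the reader gets marginal percentages and has to make the comparison unaided.

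The link to each patient's own baseline matters more here than for most variables. Protocol 4.3 requires daytime urgency incontinence and frequency, but no night-time wetting. Randomisation (Protocol 5.4) is stratified on daytime episodes only. The zero-nights row at week 12 therefore pools patients who were never wet at night with patients who became dry, and only the second group shows a possible treatment effect. The diary (Protocol 6.3.5) records night-time wetting at screening and before each clinic visit, so the data to separate them exist.

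At stake is how precisely, and how safely against chance imbalance, a dose effect on this one variable can be read. The SAP's amendment table says that recruitment was stopped, so groups may be smaller than the planned 32.

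**Working it through.** **1. The plan's own figures.** For the primary variable, the half-width is 1.96 × SD × √(2/32) = 0.49 × SD. For SDs of 2.0, 2.5, 3.0, 3.5 and 4.0 this gives 0.980, 1.225, 1.470, 1.715 and 1.960, as in SAP 1.3. Enrolment is 32/0.9 = 35.6, rounded up to 36, and 36 × 3 = 108, also as stated. No precision is given for night-time incontinence.

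**2. The six variables of Protocol 7.2.2, as analysed in SAP 5.4 for cycle 1.**

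| Variable | SAP | Dose contrasts vs 25 U | Own baseline used |
|---|---|---|---|
| Micturition episodes | 5.4.1 | ANCOVA | yes |
| Urgency episodes | 5.4.2 | ANCOVA | yes |
| Volume per micturition | 5.4.3 | ANCOVA | yes |
| PinQ | 5.4.5 | ANCOVA | yes |
| Modified TBS | 5.4.6 | CMH | has no baseline |
| Night-time incontinence | 5.4.4 | none | baseline shown by group only |

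**3. Chance imbalance at baseline.** The SD of the difference in % wet between two groups is √(2p(1−p)/n), where the baseline rate p is an assumption.

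- n = 32: √(2 × 0.3 × 0.7/32) = 11.5 points; √(2 × 0.5 × 0.5/32) = 12.5 points. The exact binomial chance of a gap of at least 20 points is 7.5% to 10%.
- n = 20: SD 14.5 to 15.8 points; the chance of such a gap is 23% to 27%.

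**4. What the marginal rows cannot give.** Suppose that in one group of 32, 50% are wet at baseline (16 wet, 16 dry) and about 30% at week 12 (10 wet, 22 dry). Two different histories produce these rows:

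- 6 became dry and none became wet. The SE of the change is √{[6/32 − (6/32)²]/32} = √(0.1523/32) = 6.9 points.
- 16 became dry and 10 became wet. The SE is √{[26/32 − (6/32)²]/32} = √(0.7773/32) = 15.6 points.

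The table is identical in both cases. A crude interval for the week 12 difference can be computed from it, but a valid interval for a baseline-corrected difference cannot.

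**5. What adjustment would gain.** These are simulated SEs of the difference in % dry on both nights, 32 per group, for assumed correlations r between baseline and week 12. The last column is the linear-model approximation 1 − √(1 − r²).

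| r (about) | Crude SE | Adjusted SE | Reduction | Approximation |
|---|---|---|---|---|
| 0.25 | 11.8 | 11.7 | 1% | 3% |
| 0.4 | 12.2 | 11.4 | 7% | 8% |
| 0.6 | 12.1 | 9.9 | 18% | 20% |
| 0.75 | 12.3 | 8.6 | 30% | 34% |

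The simulated gains follow the approximation and lie slightly below it.

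**6. Power.** A separate simulation analysed the number of wet nights, using a patient random effect and an assumed dose effect of 1.5 on the log-odds scale. Power moved as follows, unadjusted to adjusted:

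- n = 32: 73% to 81% (r about 0.4), 44% to 63% (0.6), 23% to 45% (0.75).
- n = 20: 52% to 58%, 29% to 41%, 16% to 29%.

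With no dose effect, both methods rejected in about 5% of trials. In the 7% to 10% of such trials (n = 32) where the higher dose started at least 0.3 nights better, the unadjusted test was nominally significant in 10% to 21% and the adjusted test in about 6%.

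**The case against.** The strongest reply is that the descriptive treatment is deliberate and consistent. SAP 5.4.4 matches Protocol 7.3.2.2, and specific text normally governs general text. The Protocol Summary's similar analysis is an ANCOVA, which does not fit a presence/absence variable. Protocol 7.3.3.1 refers back to Section 7.3.2, where this variable has its own descriptive sentence. The SAP 5.1 sentence on change from baseline follows a list that includes the TBS and the retreatment times, which have no baseline, so it cannot cover every item. This stands in part. A reader might infer that the SAP breaches the protocol, but the documents show only general statements that the specific sections do not carry out.

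A second reply is that the baseline is visible: the SAP says "nights will be presented by treatment group for study baseline and each post-treatment visit". A reader can subtract each group's baseline percentage. This also stands in part. In one scenario with strongly persistent wetting (40% wet at baseline, each wet night resolving with probability 0.3 at 25 U and 0.6 at 100 U, 32 per group), the SE was 11.3 points for week 12 alone, 9.7 after subtraction and 8.3 with stratification on baseline. Subtraction therefore recovers (11.3 − 9.7)/(11.3 − 8.3) = 53% of the gain. It still gives no valid interval (step 4). It is also inexact when patients are missing at week 12, because SAP 5.4 does not impute secondary variables.

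Third, this is not the only secondary measure without a dose test. The times to request and to qualify for retreatment (Protocol 6.1.2) get Kaplan-Meier estimates and medians with no stated test (SAP 5.5.1). The contrast drawn here holds only within the six variables of Protocol 7.2.2.

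**Conclusion.** The point holds as a minor one. Five of the six week 12 secondary variables get dose comparisons and night-time incontinence does not. The reason is not stated, and the general statements in the Protocol Summary and SAP 5.1 point the other way.

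A reader might go further and conclude that the planned table is biased, or that the trial fails to answer its own question. The documents do not support either. Randomisation keeps the crude comparison unbiased on average, with type I error near 5%. The efficacy hypothesis in Protocol 2.2 concerns daytime incontinence only, and this variable lies outside the hierarchical test. The primary conclusion is unaffected.

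The size of the loss is uncertain because the documents give no night-time rates or correlations. Under the assumed correlations of about 0.25 to 0.75, the SE reduction forgone at 32 per group ranges from about 1% to 30%. At the low end, the shift table and the interval are the only real benefits. Smaller groups would limit power whatever the method.

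**What to change.** In SAP 5.4.4, for cycle 1 up to week 12:

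- Add a baseline-by-visit shift table of wet nights (0, 1, 2) by dose group.
- Compare 100 U with 25 U and 50 U with 25 U on being dry both nights, using a baseline-adjusted method and a 95% interval. One option is CMH stratified by baseline night-time status (wet or dry). Another is a logistic or ordinal model with baseline wet nights and the randomisation stratum.
- Say how the randomisation stratum is handled, since the other compared secondary variables use it.
- Label the results as secondary, without multiplicity adjustment, as for the other five.

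If CMH is used, wet/dry is safer than three baseline strata. With an assumed 15% to 20% of patients wet on exactly one night, that stratum would hold 0.15 × 20 = 3 to 0.20 × 32 = 6 patients per arm.

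If the sponsor prefers to keep the variable descriptive, the SAP should say so and reconcile this with the Protocol Summary and SAP 5.1.

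The cost is SAP wording, one table and two comparisons per visit, with no new data. The downside is two more unadjusted secondary p-values at each visit compared, and limited power if groups fall below 32. The present count table can stay for later cycles.
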